8.8 Secondary Endpoints and Associated Hypotheses

All secondary endpoint analyses and associated hypotheses will be conducted on the Per Protocol Analysis Set.

If the primary endpoint analysis successfully demonstrates non-inferiority of femoral broaching time, regardless of whether the above test of superiority was successful or not, then the following three secondary endpoint analyses will be conducted under a gatekeeping strategy, in this specified order, where testing is performed in sequence and continues until a null hypothesis is not rejected or all hypotheses have been tested, each with a 1-sided alpha of 0.05:

- 8.8.1 Skin-to-skin OR time
 - Skin-to-skin OR time in minutes will be summarized as a continuous variable for both treatments and combined
 - A non-inferiority test of skin-to-skin OR time will be conducted with a noninferiority margin of 3.75 minutes, using a 2-sample t-test:
 - Null Hypothesis: $H_0: \mu_I \ge \mu_C + 3.75$
 - Alternative Hypothesis: H_A : $\mu_I < \mu_C + 3.75$
 - where μ_I and μ_c are mean skin-to-skin OR times with and without KINCISE, respectively. The null hypothesis will be rejected and non-inferiority will be concluded if the 1-sided upper 95% confidence limit for the μ_I μ_c difference (based upon a 2-sample t-test) is less than 3.75
 - The 1-sided upper 95% confidence limit for the difference and the pvalue will be presented.
- 8.8.2 The percent of subjets with acetabular cup abduction angle within +/- 10 degrees of plan
 - The proportion of subjets with acetabular cup abduction angle within +/- 10 degrees of plan will be summarized for both treatments and combined
 - A non-inferiority test of the percent of subjects with acetabular cup abduction angle within +/- 10 degrees of plan under a NI margin of 10% will be conducted:
 - Null Hypothesis: $H_0: P_I \le P_C 10\%$
 - Alternative Hypothesis: $H_A: P_I > P_C 10\%$
 - where P_I and P_c are the percentages of subjects with acetabular cup abduction angle within 10% of plan with and without KINCISE, respectively. The null hypothesis will be rejected and non-inferiority will be concluded if the 1-sided lower 95% confidence limit for the P_I –

 P_{C} difference (based upon a normal approximation method) is greater than -10%

- The 1-sided lower 95% confidence limit for the difference and the pvalue will be presented.
- 8.8.3 The percent of subjects with acetabular cup version angle within +/- 10 degrees of plan
 - The proportion of subjets with acetabular cup version angle within +/- 10 degrees of plan will be summarized for both treatments and combined
 - A non-inferiority test of the percent of subjects with acetabular cup version angle within +/- 10 degrees of plan under a NI margin of 10% will be conducted:
 - Null Hypothesis: $H_0: P_I \le P_C 10\%$
 - Alternative Hypothesis: $H_A: P_I > P_C 10\%$
 - where P_I and P_c are the percentages of subjects with acetabular cup version angle within 10% of plan with and without KINCISE, respectively. The null hypothesis will be rejected and non-inferiority will be concluded if the 1-sided lower 95% confidence limit for the P_I P_c difference (based upon a normal approximation method) is greater than -10%.
 - The 1-sided lower 95% confidence limit for the difference and the pvalue will be presented.
- 8.8.4 The percent of subjects with both acetabular cup abduction angle within +/- 10 degrees of plan and acetabular cup version angle within +/- 10 degrees of plan will be summarized for both treatments and combined.

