Confidential Version Date: 040CT2021 DePuy Synthes Protocol DSJ_2019_03 / Version 2.0 / TV-eFRM-02920 Page **16** of **53** assignment and as documented in the source and eCRF). However, KINCISE must be used for the femoral broaching per the randomization assignment; if not, then this would be a protocol deviation. For those subjects randomized to the control group (mallet), the mallet must be used for all steps throughout the surgery.

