5.2 Study Database

The study database has been validated in accordance with 21 CFR Part 11. Prior to being released for importation of study data, validation of the study level components will be conducted in accordance with approved user acceptance testing procedures. Access to this system will be controlled so that only authorized users will have the ability to enter into the system. The system is considered a closed system according to 21 CFR Part 11 Electronic Records; Electronic Signatures.

6 Radiographs

The radiographs collected for this study will be sent to Medical Metrics, Inc. (MMI) for third party review. This study will accept radiographs for the preoperative interval taken prior to the study Subject's participation in this study up to 180 days before surgery as long as the radiographs meet the three

Confidential Version Date: 040CT2021 DePuy Synthes Protocol DSJ_2019_03 / Version 2.0 / TV-eFRM-02920 Page **22** of **53** protocol required views: Antero-Posterior (AP) Long Leg or AP Pelvis (bilateral), AP Hip (unilateral), and Lateral. Preoperatively, weight-bearing AP Pelvis and AP Hip and Modified Lauenstein views are preferred, but not required. The 180 day preoperative window is allowed in order to minimize a study subject's unnecessary exposure to radiation, therefore, standard of care views will be accepted preoperatively if imaging has already been acquired before the subject was consented for the study. For all post-operative intervals, weight-bearing AP Hip and AP Pelvis, and Lateral films are required. The Modified Lauenstein view is preferred postoperatively but a Lauenstein lateral or cross-table lateral view will be accepted in instances where the view cannot be collected due to subject positioning constraints. Further radiographic details will be available in the radiographic protocol separate to this document.

7 Subject Evaluations

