10.9.4 Secondary Endpoints

All secondary endpoint analyses will be performed on the Per Protocol Population.

Skin-to-skin OR time in minutes will be summarized as a continuous endpoint for both treatments. The difference in means $\mu_I - \mu_C$ will also be summarized as a continuous endpoint. Its 1-sided upper 95% confidence limit and the p-value for the test of non-inferiority with a margin of 3.75 based on a 2-sample t-test will be produced if the alternative hypothesis of non-inferiority of the primary endpoint is rejected.

The difference between acetabular cup abduction angle and plan for each subject will be summarized as a continuous endpoint for both treatments. The proportion of subjects with acetabular cup abduction angle within 10% of plan will be summarized as a categorical endpoint for both treatments. The difference in proportions $P_I - P_C$ will also be summarized as a categorical endpoint. Its 1-sided lower 95% confidence limit and the p-value for the test of non-inferiority with a margin of 10% based upon a normal approximation method will be produced if the alternative hypothesis of non-inferiority of skinto-skin OR time is rejected.

The difference between acetabular cup version angle and plan for each subject will be summarized as a continuous endpoint for both treatments. The proportion of subjects with acetabular cup version angle within 10% of plan will be summarized as a categorical endpoint for both treatments. The difference in proportions $P_I - P_C$ will also be summarized as a categorical endpoint. Its 1-sided lower 95% confidence limit and the p-value for the test of non-inferiority with a margin of 10% based upon a normal approximation method will be produced if the alternative hypothesis of non-inferiority of acetabular cup abduction angle within 10% of plan is rejected.

With no prospectively planned hypotheses, the following secondary endpoints will be summarized at all visits with available data for both treatments as continuous variables:

- The Harris Hip Score (HHS) and change from baseline HHS
- Forgotten Joint Score (FJS) and change from 6-week postoperative FJS
- EQ-5D-5L and change from baseline
- Pain (Groin, Thigh, and Buttock)
- Patient Satisfaction
- Radiographic Outcomes (based upon: AP Hip, AP Pelvis, and Lateral)
- Length of hospital stay after index THA

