10.9.5 Safety Analyses

All safety analyses will be performed on the Safety Population set.

All Adverse Events (AE) from the start of device placement until subject finishes participation in the study will be summarized with frequencies, number of subjects with at least one AE, and percentages for the following categories: Overall, SAE, death, device and procedure related. AEs will also be summarized by Preferred Term within System Organ Class for overall for all reported AEs as well as for the subset of SAEs.

Re-hospitalizations during the study within 90 days post-op and complications within 90 days post-op will be summarized.

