8.8.9 Hip Evaluation Functional Recovery Outcomes

All questions on the hip evaluation functional recovery outcomes will be summarized as categorical data using the Per Protocol Analysis Set in the following fashion: recovery time will be the first week (Week 1 – After Week 12) recovery was achieved; Otherwise, recovery time will be "Still cannot do" or "Not Applicable/I never do this" if subject selected these options at the last visit subject was seen.

8.8.10 Radiographic Outcomes (based upon: AP Hip, AP Pelvis, and Lateral) at week 6, week 24

The following radiographic endpoints will be summarized at week 6 and at week 24: Acetabular cup version – Hip, Acetabular cup version – Pervis, Acetabular cup Inclination, Acetabular cup migration, Acetabular cup radiolucency, Acetabular cup osteolysis, Acetabular cup scerotic lines, Acetabular cup porous coating integrity, Femoral stem position, Femoral stem tilt, Femoral stem subsidence, Femoral stem radiolucency, Femoral stem osteolysis, Femoral stem osteolytic lines, Femoral stem coating integrity, Calcar resorption, Calcar fracture, Heterotopic ossification, Proximal femur, Pelvis vertical alignment, Device/anatomy condition.

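### Third-party radiographic harm readings are summarised on the Per Protocol set only, with no table covering all treated hips

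*SAP*

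**What the plan says.** **Analysis set.** SAP 8.8: "All secondary endpoint analyses and associated hypotheses will be conducted on the Per Protocol Analysis Set". Protocol 10.9.4: "All secondary endpoint analyses will be performed on the Per Protocol Population", and radiographic outcomes are in that section's list.

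**Radiographic items.** SAP 8.8.10: "The following radiographic endpoints will be summarized at week 6 and at week 24". Its list includes "Femoral stem subsidence, Femoral stem radiolucency, Femoral stem osteolysis" and "Calcar resorption, Calcar fracture, Heterotopic ossification", as well as stem tilt and cup migration. It names no analysis set. Under Protocol section 6 the films go to an outside company "for third party review".

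**Where the SAP uses another set.** The narcotic listing (8.8.11) is on the Safety set. Demographics, operative details and post-operative details (8.3 to 8.5) are shown on both the Safety and the Per Protocol sets. SAP 8.13 plans no sensitivity analysis.

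**Safety.** Protocol 10.9.5: "All safety analyses will be performed on the Safety Population set". SAP 8.9 does the same for adverse events. Protocol Table 8-1 gives radiolucent lines at the femoral component as an example of a device-related SAE.

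**Membership.** Under SAP section 6, a Per Protocol subject must have received the planned treatment successfully, met the eligibility criteria, been seen at one or more post-operative visits, and had no deviation judged in advance to threaten validity. *Successfully* is not defined, and eligibility breaches are the only disqualifying deviations given as an example. Protocol 3.4 adds: "KINCISE must be used for the femoral broaching per the randomization assignment; if not, then this would be a protocol deviation". In the KINCISE arm, documented mallet use at other steps is not a deviation.

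**The concern.** The 8.8.10 items named above are possible harms of impaction and fixation, yet they are handled as efficacy-type secondary endpoints. The same finding, for example a radiolucent line at the stem, is tabulated on the Safety set if the investigator reports it as an AE. If only the outside reader sees it, it is tabulated on Per Protocol alone.

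Per Protocol selection is not neutral for these items. Membership depends on events in the operating room, and in the KINCISE arm the stated deviation sits at femoral broaching, a step where femoral damage could plausibly arise. The trial is open-label once treatment is assigned (SAP section 3), so the independent film reading is a useful check on AE reporting by investigators who know the treatment. A table of that reading that leaves out hips because of how the surgery went could give a distorted harm comparison.

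**Working it through.** The plan gives no number on this point, so there is no stated figure to reproduce. The check is a reading of the set definitions, followed by an illustration on assumed rates.

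**1. Which set governs 8.8.10.** It names none, so the 8.8 rule applies, and Protocol 10.9.4 agrees. Because 8.8.11 names a different set explicitly, silence in 8.8.10 cannot be read as an exception. Result: Per Protocol only.

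**2. Which KINCISE-assigned hips leave Per Protocol.** Treatment received is defined twice. Protocol 10.2 says KINCISE if the device was used for broaching, otherwise MALLET. SAP section 2 says KINCISE if it was used at any time for broaching or stem impaction or both.

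| What happened | Received, Protocol 10.2 | Received, SAP 2 | Per Protocol |
|---|---|---|---|
| KINCISE used for neither broaching nor stem | MALLET | MALLET | Out |
| Mallet broaching, KINCISE stem impaction | MALLET | KINCISE | Out on the protocol definition; on the SAP definition, depends on whether the broaching deviation disqualifies |
| KINCISE broaching begun, then converted | KINCISE | KINCISE | Open: turns on *successfully* and on an unlisted set of deviations |
| KINCISE broaching completed, mallet elsewhere as needed | KINCISE | KINCISE | In, if other criteria are met |

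SAP Table 10.1 does not list the changed definition among its substantive changes.

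**3. Possible size (illustration; every rate and count is an assumption).** Take 200 hips assigned to KINCISE, all with films. Let *a* be the number excluded from Per Protocol, *r0* the harm rate in the rest and *r1* the rate in the excluded hips.

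- Per Protocol rate = *r0*
- Assigned-arm rate = [*r0*(200 − *a*) + *r1*·*a*] / 200
- Share of events missing from the Per Protocol table = *r1*·*a* / [*r0*(200 − *a*) + *r1*·*a*]

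With *r0* = 1%, the Per Protocol table shows 1.0% throughout. Each cell gives the assigned-arm rate and the missing share:

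| *a* | *r1* = 10% | *r1* = 25% | *r1* = 50% |
|---|---|---|---|
| 4 (2%) | 2.36/200 = 1.2%; 17% | 2.96/200 = 1.5%; 34% | 3.96/200 = 2.0%; 51% |
| 10 (5%) | 2.90/200 = 1.5%; 34% | 4.40/200 = 2.2%; 57% | 6.90/200 = 3.5%; 72% |
| 20 (10%) | 3.80/200 = 1.9%; 53% | 6.80/200 = 3.4%; 74% | 11.80/200 = 5.9%; 85% |

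If *r1* also equals 1%, the two rates agree at 1.0%. If converted hips stay in Per Protocol, *a* = 0 and nothing is lost.

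In whole counts: 10 excluded hips with 2 calcar fractures, and 2 among the other 190, give an assigned-arm rate of 4/200 = 2.0% and a Per Protocol rate of 2/190 = 1.05%. With 4 excluded hips and 1 fracture, and 2 among the other 196, the rates are 3/200 = 1.5% and 2/196 = 1.02%.

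**4. Why the grouping matters.** The Safety set groups by actual treatment. If the 10 hips above were excluded because they received MALLET, the Safety-set KINCISE rate would also be 2/190 = 1.05%. With *c* fractures among 200 control hips, the MALLET rate would become (*c* + 2)/210. So 4/200 and 3/200 are assigned-arm rates. They equal Safety-set rates only if the excluded hips count as KINCISE received.

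**The case against.** The strongest reply is that the Safety set already covers most of the ground, and that the exclusions may be few.

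- Reported AEs and SAEs are tabulated there with a subject-level listing (SAP 8.9). Intraoperative complications, wires or cables, and the steps done with KINCISE or mallet are shown on both sets (SAP 8.4). Complications within 90 days are summarised on the Safety set (Protocol 10.9.5), and a cup or stem revision requires an AE form (Protocol 3.5.5). This stands. It narrows the gap to independently read findings that were not also reported as AEs, in hips outside Per Protocol.
- A reader might infer that every hip in which KINCISE broaching was abandoned vanishes from the film tables. The documents do not say so. A hip begun with KINCISE and then converted counts as KINCISE received under both definitions and may stay in Per Protocol.
- A reader might also infer that the comparison is biased in favour of KINCISE. That is not shown. Per Protocol exclusions apply to control hips too, where the mallet is required at every step, and no exclusion or harm rate is given for either arm.
- Some of the worst cases have no films to recover. Subjects withdrawn intraoperatively are not followed and are replaced (Protocol 3.5.2 and 3.5.3), and those with a revised cup or stem leave the study (3.5.5). This also stands, and it limits what any re-tabulation can do.

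None of this supplies an all-treated table of the outside reader's findings.

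**Conclusion.** The point holds as a gap in reporting. The third-party readings of the 8.8.10 harm items are planned on Per Protocol only, and membership of that set depends partly on how surgery went. KINCISE-assigned hips not broached with KINCISE can drop out. Hips converted part-way may or may not, because the deciding word is undefined.

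The effect on the harm comparison cannot be computed from the documents, in direction or size. Under the assumed rates above it runs from nil to a Per Protocol rate of 1.0% against an assigned-arm rate of 5.9%. The upper end needs 10% of hips excluded and half of them harmed, which nothing in the documents supports as likely.

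The radiographic harm items carry no hypothesis, so no test, sample size or power figure is affected. The change is worth making because it costs little and removes a possible selection effect from a harm table.

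**What to change.** 1. In SAP 8.8.10, summarise the radiographic harm items for all treated hips with films, by assigned arm and by treatment received. Keep the Per Protocol table as supportive. The assigned-arm view is needed because grouping by treatment received alone would count a fully converted hip under MALLET.
2. Before analysis, define what receiving the planned treatment successfully means, including for broaching begun with KINCISE and then converted, and list the disqualifying deviations.
3. Reconcile the treatment-received definitions in Protocol 10.2 and SAP section 2, and record the outcome in SAP Table 10.1 if it departs from the protocol.
4. State beside the tables how many treated hips in each arm have no films and why, including intraoperative withdrawals and revisions.
5. Leave the cup-angle non-inferiority tests as planned.

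The cost is a few sentences in the SAP and one extra set of tables from data already being collected. No new visits, films or readings are needed.

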Based upon input from KOLs and data from other studies, skin-to-skin OR time is anticipated to have a typical range from 60 to 90 minutes, which implies a standard deviation of approximately 7.5 minutes (1/4 of the range). The non-inferiority margin of 3.75 minutes was established because it is ½ of the anticipated standard deviation and is much less than the 10 minute clinically meaningful difference in femoral broaching time (a subset of skin-to-skin OR time). Under a 1-sided test with 5% alpha, a sample size of N=200 per group would be sufficient to demonstrate non-inferiority with greater than 99% power.

• Non-inferiority of optimal acetabular cup abduction

The percent of subjects within +/- 10 degrees of planned cup abduction for an anterior approach (AA) is anticipated to be between 90% and 95% (based on studies presented by Hamilton¹ and Rathod², respectively). These are a clinical improvement from percentages exhibited with a posterior approach (PA), which were 79% and 86% in [1] and [2], respectively. A NI margin of 10% was chosen because it is less than the improvement from PA to AA observed by Hamilton¹ and

Rathod². With this margin and a 1-sided test with 5% alpha, a sample size of N=200 per group would be sufficient to demonstrate non-inferiority with approximately 95% power.

• Non-inferiority of optimal acetabular cup abduction

The percent of subjects within +/- 10 degrees of planned cup version for an anterior approach (AA) is anticipated to be between 91% and 92% (based on studies by Rathod² and Hamilton¹, respectively). These are a clinical improvement from percentages exhibited with a posterior approach (PA), which were 64% and 77% in [1] and [2], respectively. A NI margin of 10% was chosen because it is less than the improvement from PA to AA observed by Hamilton¹ and Rathod². With this margin and a 1-sided test with 5% alpha, a sample size of N=200 per group would be sufficient to demonstrate non-inferiority with approximately 95% power.

In summary, with a sample size of N=400 (200 with KINCISE; 200 without KINCISE), the anticipated overall likelihood of demonstrating the primary endpoint non-inferiority analysis, followed by the three stated secondary endpoint non-inferiority analyses in the specified gate-keeping order, is at least $(99\%)(99\%)(95\%)(95\%) \approx 88\%$.

8 Analyses to be Conducted

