8.12 Adjustment for Multiplicity

A gatekeeping strategy will be utilized to ensure the family-wise type I error rate does not exceed 5% for all pre-specified hypotheses: the test of non-inferiority of the primary endpoint will be performed at the 95% confidence level and all subsequent hypotheses in the order specified in sections 8.7 and 8.8 will be tested only if the prior null hypothesis was rejected. P-values and confidence intervals for analyses which were not tested will not be adjusted for multiplicity and may only be provided to facilitate clinical judgement.

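### The unnamed normal-approximation limit for the two cup-angle tests, read as the unpooled limit, runs slightly above its one-sided 5% (5.25% to 5.46% at the planned rates); naming the Miettinen-Nurminen score limit corrects this cheaply

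*SAP*

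**What the plan says.** SAP 8.8.2 (abduction) and 8.8.3 (version) test whether the percentage of cups within 10 degrees of plan is non-inferior with KINCISE, using a margin of 10 percentage points. Non-inferiority is concluded if the one-sided lower 95% limit for the difference, "based upon a normal approximation method", lies above minus 10%. Protocol 10.5.2 and 10.9.4 use the same method. Neither document states the variance form, a score method or a continuity correction.

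The two tests are third and fourth in the gatekept order, after broaching time and skin-to-skin time, "each with a 1-sided alpha of 0.05". SAP 8.12 says the gatekeeping will "ensure the family-wise type I error rate does not exceed 5" percent.

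SAP 7 plans 200 per group. The abduction success rate "is anticipated to be between 90% and 95" percent, and the version rate "is anticipated to be between 91% and 92" percent. Each test is credited with about 95% power. SAP 8.13 plans no sensitivity analyses.

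**The concern.** Ordered testing protects the family-wise error only if each test in the sequence holds its own level. The unpooled limit estimates the variance from the observed rates. In samples close to being declared non-inferior, the observed KINCISE rate sits nearer to control than the null allows. At success rates this high, that makes the standard error too small. The lower limit then sits too high, so the test errs towards declaring non-inferiority.

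These are two formal, alpha-controlled claims, and no alternative interval is planned beside them. A borderline result that depends on the choice of limit would therefore go unnoticed. The unnamed variant also leaves that choice to the analyst.

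**Working it through.** **Inputs.** n = 200 per arm; control rates P_C of 90% to 95% (abduction) and 91% to 92% (version), from SAP 7; margin 0.10 and one-sided alpha 0.05 (z = 1.645), from SAP 8.8.

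**Step 1: reproduce the stated power.** With equal true rates p and unpooled variance, power = Φ(0.10 / √(2p(1−p)/200) − 1.645).
- p = 0.90: SE = 0.0300, so Φ(3.333 − 1.645) = 95.4%.
- p = 0.91: 96.8%; p = 0.92: 97.9%; p = 0.95: 99.8%.

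The plan's 95% appears at the low end of the range. A two-sided 5% version gives 91.5% at 0.90 and does not match. This supports reading the plan's method as the unpooled limit.

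**Step 2: exact type I error.** Non-inferiority is declared when p̂_I − p̂_C − 1.645·√[p̂_I(1−p̂_I)/n + p̂_C(1−p̂_C)/n] > −0.10. The binomial probabilities of all 201 × 201 outcomes that meet this rule are summed at P_I = P_C − 0.10 for type I error, and at P_I = P_C for power. The score limits replace the variance with its restricted maximum-likelihood estimate under a true difference of −0.10. Miettinen-Nurminen also multiplies that variance by N/(N−1), with N the total of both arms.

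| P_C | Error: unpooled | Error: Farrington-Manning | Error: Miettinen-Nurminen | Power: unpooled | Power: Miettinen-Nurminen |
|---|---|---|---|---|---|
| 0.90 | 5.25% | 4.99% | 4.89% | 95.24% | 94.80% |
| 0.91 | 5.31% | 5.03% | 4.87% | 96.54% | 96.17% |
| 0.92 | 5.35% | 5.06% | 4.87% | 97.68% | 97.33% |
| 0.95 | 5.46% | 4.91% | 4.90% | 99.74% | 99.61% |

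The unpooled limit is above 5% at every point of a fine grid of control rates from 90% to 100%. Miettinen-Nurminen is below 5% throughout 90% to 95%. A simulation of 1,000,000 trials per point gave 5.28% and 5.48% for the unpooled limit at 0.90 and 0.95, in agreement.

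**Step 3: one outcome where the methods disagree.** Take 179/200 with KINCISE and 190/200 without; the difference is 0.895 − 0.950 = −0.055.
- Unpooled: SE = √(0.895×0.105/200 + 0.950×0.050/200) = 0.02660. The limit is −0.055 − 1.645×0.02660 = −0.0987, so non-inferiority is declared.
- Miettinen-Nurminen: the restricted rates are 0.861 and 0.961. SE = √[(0.861×0.139 + 0.961×0.039)/200 × 400/399] = 0.0281. Then z = (0.10 − 0.055)/0.0281 = 1.60, below 1.645, so non-inferiority is not declared.

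**Step 4: does the gate absorb the excess?** Under the plan's own assumptions and equal means, each of the two earlier non-inferiority tests has power Φ(5 − 1.645) = 99.96%, since 1.25/(2.5·√(2/200)) = 3.75/(7.5·√(2/200)) = 5. The gate therefore stays shut with probability of at most 2 × 0.04% = 0.08%. Within the non-inferiority sequence, the error remains at least 5.25 − 0.08 = 5.17% at 90% and 5.46 − 0.08 = 5.38% at 95%.

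**The case against.** The strongest reply is that the plan never says unpooled. A score limit is itself a normal approximation, and so is a continuity-corrected limit, which gives only 3.9% to 4.0% over the planned rates at 200 per arm. This stands: the excess is conditional on the unpooled reading. That reading is the natural one and fits the stated power, but the wording does not compel it. Leaving the variant unnamed is a gap under any reading.

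The size is also open to challenge: under half a point, on the third and fourth gated tests, while study success rests on broaching time alone. That stands too, and it sets the severity.

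A reader might infer two stronger claims that the documents do not support.
- **That the error is 6% to 7%.** The unpooled limit gives 5.84% at a control rate of 97%, 6.34% at 98% and 7.07% at 99%, but SAP 7 anticipates no more than 95%.
- **That the excess grows as the Per Protocol set shrinks.** The documents give no attrition figure, so any smaller set is an assumption. At 200, 190, 180 and 160 per arm the error is 5.25%, 5.35%, 5.26% and 5.32% at a 90% control rate, and 5.46%, 5.67%, 5.75% and 5.62% at 95%. It moves with the discreteness of the binomial and shows no consistent rise.

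**Conclusion.** The point holds as a minor one. On the unpooled reading with 200 per arm, the true one-sided error of each cup-angle test is 5.25% to 5.46% over the anticipated rates, always in the direction of declaring non-inferiority. Read literally, the 5% ceiling in SAP 8.12 is not met. The figures assume independent binomial outcomes, equal arms and a true difference exactly at the margin. At that boundary only the control rate is at the anticipated level; the KINCISE rate is 10 points lower.

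It would be wrong to infer that the trial's main conclusion is at risk, because the primary endpoint is a comparison of mean times and does not use this limit. Nor does every score limit satisfy the 5% ceiling: Farrington-Manning slightly exceeds it in the version range (5.03% to 5.06%).

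**What to change.** In SAP 8.8.2 and 8.8.3, and in Protocol 10.5.2 and 10.9.4, name the Miettinen-Nurminen score limit for the difference in proportions. Take the p-value from the same statistic so that limit and p-value cannot disagree. Keep one-sided 5%, the 10-point margin and 200 per arm.

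The cost is a programming choice and a little power. At a 90% rate with 200 per arm, power goes from 95.2% to 94.8%, so the stated figure of about 95% still holds. At 95% it goes from 99.7% to 99.6%. If the Per Protocol set were smaller, the cost at 90% would be about 0.8 points at 190 per arm (94.5% to 93.7%) and about 1.0 point at 180 (93.6% to 92.7%); both sizes are assumed. A continuity correction would also hold the level over the planned rates, but it costs more: 95.2% to 93.6% at 90% with 200 per arm.
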